7.2.2.2 Frequency

The frequency of the AE should be indicated according to the following definitions:

- **Single:** Experienced once, without recurrence
- **Recurrent:** More than one discrete episode with the same severity

7.2.2.3 Action Taken with Study Drug

- **Dose not changed:** No change in study drug
- **Drug interrupted:** Study drug temporarily stopped
- **Drug withdrawn:** Study drug discontinued permanently
- **Not applicable**
- **Unknown**

7.2.2.4 Therapy

- **None:** No new treatment instituted
- **Medication:** New treatment initiated as a direct result of AE
- **Other:** Other action required

7.2.2.5 Outcome

- **Recovered/resolved:** Recovered or resolved
- **Recovered/resolved with sequelae:** Recovered or resolved with sequelae
- **Not recovered/not resolved:** Not recovered or not resolved
- **Fatal:** Death due to an AE
- **Unknown:** Unknown

7.2.2.6 Seriousness

- Not serious
- Serious

7.2.3 Definition of Unexpectedness

An AE, the nature or severity of which is not consistent with the information provided in the Reference Safety Information section of the current pimavanserin Investigator's brochure.

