Note: A schematic for study drug dispensing and dose adjustments is provided in [Figure S-2](#)

Figure S-2 **Schematic for Study Drug Dispensing and Dose Adjustments**

* Week 2 (Visit 4) & Week 3 (Visit 5): Subjects may remain on blinded study drug dose consistent with 50 mg quetiapine or be optionally increased to 100 mg quetiapine.

Abbreviations: EOT=end of treatment; R=randomization

Note: Dose adjustments and study drug dispensing are only allowed at scheduled visits (i.e., not at unscheduled visits). Subjects should not take study drug on the mornings of clinic visit days until instructed to do so by the site staff. At Baseline and at each subsequent clinic visit, subjects will be dosed and will remain in the clinic for observation for a minimum of 60 minutes after dosing. At Week 1 (Visit 3), Week 2 (Visit 4), and Week 3 (Visit 5), the Investigator will be encouraged to increase the dose of blinded study drug, consistent with 50-100 mg quetiapine, based on the Investigator's assessment of clinical response. Dose adjustments will be implemented through the IRT. In actuality, only the dose of quetiapine would be increased (to 50 mg at Week 1 [Visit 3] and then optionally to 100 mg at Week 2 [Visit 4] or Week 3 [Visit 5]); the pimavanserin dose will remain fixed at 34 mg per day throughout the study. Subjects for whom the Investigator does not increase the dose of blinded study drug consistent with 50 mg quetiapine at Week 1 (Visit 3) will be withdrawn from the study and replaced. The Investigator will be blinded to study drug and thus will not know whether their decision to increase the dose of blinded study drug results in an actual increase in study drug dose. The dose of study drug (pimavanserin, quetiapine or placebo) may not be decreased. If a subject cannot tolerate their dose, they must be withdrawn from the study.

Table S-1 Schedule of Events and Assessments for ACP-103-056

	Screening	Baseline	Double-blind Treatment Period				Safety Follow-up
	-4	0	1 (Day 7)	2 (Day 14)	3 (Day 21)	4/EOT (Day 28)	8 ¹ (Day 58)
Visit Week (Study Day)	1	2	3	4	5	6/ET	7
Visit Number	0	0	±3	±3	±3	±3	±4
Visit window (days)	Clinic	Clinic	Clinic	Clinic	Clinic	Clinic	Telephone
Informed consent	X						
Inclusion/exclusion criteria	X	X					
Medical history and demographics	X						
Psychiatric and neurological history	X						
Physical examination (including neurologic examination)	X	X				X	
Training on the use of the handheld device and the actigraph ^a	X	X					

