1.2.2 Quetiapine

Quetiapine is a second-generation antipsychotic that has affinity for D₂, 5-HT_{2A}, H₁, alpha 1 and 5-HT_{1A} receptors. Its precise mechanism of action is unknown, but according to the dopamine theory of schizophrenia, antipsychotic effects might be related to the drug's ability to reduce dopaminergic neurotransmission in the mesolimbic pathway.

Quetiapine immediate-release is an orally administered antipsychotic approved in the United States for the treatment of schizophrenia, acute treatment of manic episodes associated with bipolar I disorder, depressive episodes associated with bipolar disorder, and maintenance treatment of bipolar I disorder ([Northstar Rx LLC. 2019](#)). The extended-release formulation is approved in the US for use as adjunctive treatment to antidepressant therapy of major depressive disorder. Quetiapine is also commonly used in off-label indications such as behavioral and psychological symptoms of dementia, posttraumatic stress disorder, depression psychosis in Parkinson's disease, anxiety disorders and insomnia ([El-Saifi et al. 2016](#)). In randomized controlled trials that recruited relatively younger and healthier populations, as opposed to the patients prescribed the medication in clinical

practice, the most frequent quetiapine side effects included somnolence (18%), dizziness (11%), dry mouth (9%), constipation (8%), orthostatic hypotension (4%), weight gain (5%), and lethargy dyspepsia (5%) ([El-Saifi et al. 2016](#)).

In April 2005, the US Food and Drug Administration (FDA) issued a warning about the increased risk of mortality associated with the use of second-generation antipsychotics in older adults with dementia-related psychosis, based on the analyses of 17 placebo-controlled trials. Most of the deaths were cardiovascular (e.g., heart failure, sudden death) or infectious (e.g., pneumonia) in nature. The quetiapine prescribing information also includes a warning regarding QT prolongation.

Additional information is provided in the US package insert for quetiapine ([Northstar Rx LLC 2019](#)).

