3 STUDY DESCRIPTION

3.1 Overview of Study Design

This study will be conducted as a multicenter, randomized, double-blind, placebo- and active-control, parallel-group pilot study in subjects with Parkinson's disease. Subjects with at least moderate neurobehavioral symptoms that could benefit from treatment will be included in the study. Up to 60 subjects will be randomized in a 1:1:1 ratio to pimavanserin, quetiapine, or placebo. Up to approximately 120 subjects will be screened. A maximum of 20% of subjects across treatment groups (12 subjects) will be replaced. Subject replacement may occur as described in [Section 3.1.2](#). The duration of participation for individual subjects will be approximately 12 weeks. Approximately 23 sites within the United States will participate in this study.

The study will have 3 periods:

- Screening period (7-28 days)
- Double-blind treatment period (4 weeks)
- Safety follow-up period (30 [± 4] days)

The study design schema is provided in [Figure S-1](#).

The study completion date is defined as the date the final subject, across all sites, completes their final protocol-defined assessment (Note: this includes the safety follow-up phone call). If the study is terminated for any reason, subjects remaining in the study will return to standard of care. Procedures for when a subject is lost to follow-up are provided in [Section 4.5](#).

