5 INVESTIGATIONAL PRODUCT

5.1 Investigational Product Description

The investigational product will be pimavanserin 34 mg (provided as 2×17 mg encapsulated tablets), immediate release quetiapine 25 mg (provided as 1×25 mg quetiapine encapsulated tablet and 1×placebo encapsulated tablet), quetiapine 50 mg (provided as 2×25 mg quetiapine encapsulated tablets), quetiapine 100 mg (provided as 2×50 mg encapsulated tablets), or matching placebo (2×placebo encapsulated tablets). Capsules will be administered orally as a single dose once daily.

Blinding will be maintained by encapsulation to ensure shape, color, and size match.

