7.4.2 Serious Adverse Event Reporting

The reporting of SAEs by the Sponsor or designee to the regulatory authorities is a regulatory requirement. Each regulatory authority has established a timetable for reporting SAEs based upon established criteria.

Serious AEs must be reported within 24 hours of discovery to the Sponsor or its designee; use the appropriate form for initial and/or follow-up reporting.

At a minimum, events identified by the Sponsor to require expedited reporting as serious, unexpected, and related to study drug must be brought to the attention of the responsible institutional review board/ethics committee (IRB/EC), as per applicable regulations. These will be provided by the Sponsor after their assessment. For European Union member states, the Sponsor or its designee will provide reports of SUSARs directly to the ECs, as required by local legislation. In all other countries, it is the Investigator’s responsibility to provide these expedited reports to the responsible IRB/EC. It is also the Investigator’s responsibility to notify the responsible IRB/EC regarding any new and significant safety information.

When an SAE occurs, Investigators will review all documentation related to the event and will complete the paper SAE form (for initial and/or follow-up information) and fax or email (within 24 hours of discovery) to the contact information provided on the SAE form.

Subjects will be followed through the safety follow-up period for 30 days after the last dose of study drug for any SAEs and/or other reportable information until such events have resolved or the Investigator, in conjunction with the Sponsor, deems them to be chronic or stable.

In the event of any SAE (other than death), the study subject will be instructed to contact the Investigator (or designee) using the telephone number provided in the ICF. All subjects experiencing an SAE will be seen by the Investigator or designee as soon as is feasible following the report of the SAE.

Serious AEs occurring after the safety follow-up period of 30 days after the last dose of study drug should be reported if in the judgment of the Investigator there is “a reasonable possibility” that the event may have been caused by the product.

SAEs should also be reported to the IRB/EC according to local regulations.

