19. CHANGES TO ANALYSES SPECIFIED IN PROTOCOL

Because this trial was stopped early after randomizing only 11 subjects, all of the mixed-model repeated measures analyses were changed to ANCOVA in order to minimize possible non-convergence issues.

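### Protocol 7.2.3 judges unexpectedness only against the pimavanserin brochure, so the expedited-reporting class of serious, related events in quetiapine subjects can be wrong

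*Protocol*

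**What the plan says.** Protocol 7.2.3 gives one definition of an unexpected AE for the whole trial. The test is whether the nature or severity of the event "is not consistent with the information provided in the Reference Safety Information section of the current pimavanserin" Investigator's brochure. It makes no distinction by treatment group.

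The protocol treats quetiapine as a product under test. Section 5.1 reads "The investigational product will be pimavanserin 34 mg (provided as 2×17 mg encapsulated tablets), immediate release quetiapine 25 mg" and goes on to the higher quetiapine strengths and placebo. The note to Figure S-2 in the synopsis uses the term study drug for all three: "The dose of study drug (pimavanserin, quetiapine or placebo) may not be decreased".

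Section 7.4.2 makes the definition operative. The class that must, at a minimum, go to the IRB/EC is "events identified by the Sponsor to require expedited reporting as serious, unexpected, and related to study drug". Section 5.1.5 allows a controlled sponsor group to learn the treatment of a subject with a potential SUSAR.

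A safety source for quetiapine is mentioned once, as background in 1.2.2: "Additional information is provided in the US package insert for quetiapine". It is not designated as reference safety information there or anywhere else in the protocol or SAP.

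**The concern.** Expectedness is a property of an event relative to a particular drug. Judging a quetiapine subject's event against the pimavanserin brochure answers the wrong question for that subject. It can err in two directions:

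- A serious, related event that is listed for pimavanserin but not for quetiapine is classed as expected and falls outside the expedited class.
- A labelled quetiapine reaction that the pimavanserin brochure does not list is classed as unexpected. That leads to avoidable expedited reports and possibly avoidable unblinding.

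The first direction matters more, because it may not correct itself. Section 5.1.5 offers unblinding only for a potential SUSAR, and an event already classed as expected does not obviously become one. The primary objective covers the safety of both active drugs against placebo, so the reporting rule should work for both.

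**Working it through.** The plan gives no figure on this point to reproduce. The check is a comparison of the text plus simple arithmetic on how many subjects are concerned.

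**Step 1: the possible cases.** Take a serious, related event in a quetiapine subject and classify it by which product's reference lists it.

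| Listed for | Class under 7.2.3 | Class against a quetiapine reference | Consequence |
|---|---|---|---|
| Both products | Expected | Expected | None |
| Pimavanserin only | Expected | Unexpected | Left out of the expedited class |
| Quetiapine only | Unexpected | Expected | Over-reported |
| Neither | Unexpected | Unexpected | None |

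The rule is wrong in two of the four cases, and in one of those two it could lose an expedited report. How many real events fall in those two rows depends on the brochure and the quetiapine label, which are not among the documents.

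**Step 2: subjects concerned, as planned.** Protocol 3.1 states: "Up to 60 subjects will be randomized in a 1:1:1 ratio to pimavanserin, quetiapine, or placebo". So 60 × 1/3 = 20 on quetiapine. The same section states: "A maximum of 20% of subjects across treatment groups (12 subjects) will be replaced". This agrees with 0.20 × 60 = 12. If the replacements come on top of the 60 and split evenly (an assumption), the figure is (60 + 12) × 1/3 = 24.

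**Step 3: subjects concerned, as run.** SAP 19 says: "Because this trial was stopped early after randomizing only 11 subjects". Under an even split, 11 × 1/3 = 3.7, or about 3 to 4. The actual split by arm is not given.

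**Step 4: where expectedness is used.** In 7.4.2 it applies only together with seriousness and relatedness. The TEAE summaries in Protocol 9.5.1 and SAP 14.1 use system organ class, preferred term, severity, relationship, seriousness, fatal outcome and discontinuation. None of them uses expectedness, so no planned table changes.

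**Step 5: whether naming a second reference is enough.** Suppose 7.2.3 said only that the reference for the product received applies. Before unblinding, the product is unknown, and 5.1.5 opens the code only for a potential SUSAR. An event in the second row of the table could still be set aside as expected at the blinded stage. A rule for that stage is needed as well.

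**The case against.** The strongest reply is that 7.2.3 is not the only control.

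- Under 7.4.2 every SAE reaches the sponsor within 24 hours, whatever its expectedness.
- The expedited class is stated as a minimum. SAEs also go to the IRB/EC under local regulations, and investigators must pass on significant new safety information.
- Section 5.1.5 refers to health authority guidance, and 12.1 commits to ICH E2A.
- One of the two error directions only over-reports.
- A separate safety plan might already name a quetiapine reference.

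Most of this stands, and it limits the point. A reader might infer that safety data in the quetiapine arm would go unreported. The documents do not support that: recording and sponsor notification are unaffected, and what can fail is the sponsor's onward classification. The reply does not remove the gap, however. The guidance is cited without its content, neither document mentions a safety plan, and if one exists with a different rule, it conflicts with 7.2.3 as written.

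A reader might also use the side-effect lists in 1.2.2 and 1.3.1 as proof of misclassification. For example, confusional state is named for pimavanserin but not for quetiapine, and orthostatic hypotension the other way round. That inference fails. Those are lists of frequent events, not reference safety information, and absence from them says nothing about absence from the label or brochure. Section 1.3.1 also mentions postural dizziness for pimavanserin, and 1.4 discusses its orthostatic hypotension rates.

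**Conclusion.** The point holds as a defect in a stated rule. Protocol 7.2.3 applies one drug's reference to subjects on another, and neither document designates a reference for quetiapine. The consequence is a possible wrong expedited-reporting class for serious, related events in quetiapine subjects: 20 of 60 as planned, and about 3 to 4 of the 11 randomized if the split was even.

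Two stronger readings are not supported. The primary safety analysis is not affected, because the TEAE summaries do not use expectedness. Nor does the absence of a data monitoring committee (SAP 17) enlarge the defect, since such a committee would not change how expectedness is defined.

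The conclusion rests on the text of the two documents. It assumes that the pimavanserin brochure does not itself contain reference safety information for quetiapine, and that no separate document overrides 7.2.3. Neither can be checked here, nor can it be shown that any particular event was or would be misclassified.

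**What to change.** Amend 7.2.3 in three parts:

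1. Name a reference for each active product: the pimavanserin brochure for pimavanserin, and the US package insert already cited in 1.2.2 for quetiapine.
2. While treatment is blinded, treat a serious related event as a potential SUSAR unless both references list it.
3. After the limited unblinding in 5.1.5, apply the reference for the product received.

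The second part brings an event listed only for pimavanserin to the unblinding step instead of setting it aside.

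The cost is a few sentences, submission to the IRB/EC under 10.7, and a few more sponsor-level unblindings.

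SAP 3.6 records that enrolment was halted in March 2020 and the study stopped permanently as of 24 September 2020. An amendment alone would therefore do little for the subjects already treated. The sponsor should also recheck the expectedness of any serious related events in quetiapine subjects, and correct the wording before reusing it, since the pilot is meant to guide later studies. If a separate safety plan already names a quetiapine reference, it should be reconciled with 7.2.3.

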7.3 Time Period and Frequency for Event Assessment and Follow-up

Adverse events will be recorded from the time informed consent is obtained through the safety follow-up period. All AEs must be either resolved or stable at the end of the safety follow-up period. If ongoing at the end of the safety follow-up period, the subject should be referred for appropriate treatment.

In the event that a subject discontinues and has an ongoing AE at the time of discontinuation (Section 4.4.1) or is withdrawn from the study because of an AE, the subject should be

followed and treated by the Investigator until the AE has resolved, stabilized, or a new chronic baseline has been established.

7.4 Reporting Procedures

7.4.1 Adverse Event Reporting

The Investigator must record all observed AEs and all reported AEs. At each visit, the Investigator should ask the subject a nonspecific question (e.g., “Have you noticed anything different since your last visit?”) to assess whether any AEs have been experienced since the last report or visit.

Note that any use of medication (and specifically any newly prescribed medication) during the course of a study may indicate the occurrence of an AE that may need to be recorded on both the AE and the concomitant medication page.

All AEs, serious and not serious, will be recorded on the AE eCRF page using appropriate medical terminology. Severity and relationship to study drug will be assessed by the Investigator.

When possible, clinical AEs should be described by diagnosis and not by symptoms (e.g., “cold” or “seasonal allergies” instead of “runny nose”).

All AEs, *whether or not related to the study drug*, must be fully and completely documented on the AE eCRF and in the subject’s notes.

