2.1.1 Primary Endpoint

The primary endpoint for this study is treatment-emergent adverse events (TEAEs).

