4.1 Inclusion Criteria

A subject must meet all of the following inclusion criteria to be eligible for participation in the study:

1. Male or female subjects 50 to 85 years of age, inclusive, at Screening and Baseline
2. Can understand the nature of the trial and protocol requirements and provide written informed consent
3. Is able to demonstrate the ability to complete subject-reported outcome measures on a handheld device, is willing to wear a data capture instrument (e.g., an actigraph), and can be reliably rated on assessment scales (in the opinion of the Investigator)
4. Can designate an “informant” (a relative, housemate, or friend) who the subject agrees can provide reliable information on the subject’s well-being and is willing to attend clinic visits with the subject
5. Is able to swallow the test capsule without difficulty during the Screening visit
6. Has a Mini-Mental State Examination (MMSE) score ≥ 19

7. Has a diagnosis of idiopathic Parkinson's disease, without any other known or suspected cause of parkinsonism, according to the UK Parkinson's Disease Society Brain Bank Clinical Diagnostic Criteria ([Hughes et al. 1992](#)). Initial diagnosis of PD must have been made more than 1 year prior to Screening.
8. [Inclusion criterion eliminated]
9. Has at both Visit 1 (Screening) and Visit 2 (Baseline), a CGI-S score of ≥ 3 on at least one of the following non-motor neuropsychiatric symptoms that warrant treatment with an antipsychotic agent based on Investigator judgement. Such symptoms do not need to be the same at Screening and Baseline, and all symptoms should be assessed at both Screening and Baseline.
 - a. Delusions
 - b. Hallucinations
 - c. Depression/Dysphoria
 - d. Apathy/Indifference
 - e. Disinhibition
 - f. Irritability/Lability
10. If the subject is on anti-Parkinsonian medication, they must be on a stable regimen for 1 month prior to Baseline and not planning (at the time of the Baseline visit) to make a major change in dose(s)
11. If the subject has had stereotaxic surgery for subthalamic nucleus deep brain stimulation, they must be at least 6 months post-surgery. The stimulator settings must have been stable for at least 1 month prior to the Baseline visit and are expected to remain stable during the trial.

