 - The following controlled substances may be tested with a urine toxicity screen according to the schedule presented in [Table 6–1](#): amphetamine, barbiturates, benzodiazepines, cocaine, methadone, morphine/opiates, methamphetamine, marijuana (THC), phencyclidine (PCP), ecstasy (MDMA).
 - Subjects who test positive for benzodiazepines, THC, or opiates may continue in the study and last usage should be noted at the study visit. In addition, restrictions listed in [Appendix A](#) should be followed.
 - Reasonable efforts should be made to collect a urine sample (as described in “Urinalysis” above) at all designated visits

Laboratory evaluations will be completed according to the schedule presented in Table 6–1 and procedures detailed in the study Manual of Procedures. Additional safety testing may be performed at the discretion of the Investigator or designee. All laboratory results should be evaluated for clinical significance and be reported as an AE/SAE, as applicable.

Table 6–1 Safety Laboratory Evaluations

Visit	Tests ^{a,b}
Visit 1 (Screening, Week -4)	CHEM, CBC, UA, urine toxicity screen, and serum pregnancy test
Visit 2 (Baseline, Week 0)	CHEM, CBC, UA, insulin, prolactin, urine toxicity screen, and urine pregnancy test
Visit 4 (Week 2)	CHEM, CBC, and UA
Visit 6/ET (Week 4/EOT)	CHEM, CBC, UA, insulin, prolactin (blinded), urine toxicity screen, and urine pregnancy test

Abbreviations: CBC=complete blood count; CHEM=clinical chemistry serum tests; EOT=end of treatment; ET=early termination; TSH=thyroid stimulating hormone; UA=urinalysis

^a A pregnancy test is only required for women of childbearing potential. If urine cannot be obtained in women of childbearing potential, a serum pregnancy test should be done.

^b A vitamin B12 test, HbA1c, Mg level, and TSH/free T4 test are only required at Visit 1 (Screening).

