6.4 Safety Follow-up

A 30-day safety follow-up telephone contact is to be completed for subjects who complete the treatment period of the study as well as those who discontinue prematurely from the study. Subjects should have the following completed 30 (± 4) days after last dose of study drug:

- Assessment of concomitant medications/treatments
- Assessment of AEs

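### Adverse events, the primary endpoint, are actively sought only from the subject; no text has the informant asked, so some sleepiness, confusion and behavioural events may be missed

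*Protocol*

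**What the plan says.** Treatment-emergent adverse events are the primary endpoint (protocol 2.1.1; SAP 14.1). The window runs to 30 days after the last dose.

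On collection, protocol 7.4.1 has two parts. The recording rule is broad: "The Investigator must record all observed AEs and all reported AEs". It does not limit who may report, and newly used medication is treated as a possible sign of an event. The elicitation rule is narrow: "At each visit, the Investigator should ask the subject a nonspecific question". For the follow-up telephone contact, section 6.4 lists "Assessment of AEs" without saying who is to be asked. Section 6.3.7 adds laboratory review: "All laboratory results should be evaluated for clinical significance and be reported as an AE/SAE, as applicable".

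On the subject, section 4.1 sets the cognitive floor: "Has a Mini-Mental State Examination (MMSE) score ≥ 19". Delusions and hallucinations are two of the six qualifying symptoms. Section 1.4 says low-dose quetiapine has been reported to cause daytime sedation, linked to worse cognition. Section 1.3.1 names somnolence and confusional state among events reported with pimavanserin.

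On the informant, criterion 4 of section 4.1 requires a person whom the subject accepts as a reliable source and who "is willing to attend clinic visits with the subject". Informants are blinded (5.1.5). They rate the subject's sleep, sleep-related impairment and cognition, and answer the satisfaction question (Table S-3, 6.2.1, 6.2.8). Their word can count towards compliance (5.1.6). Lack of a reliable informant is a listed reason for discontinuation (4.4).

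**The concern.** The protocol relies on the informant for sleep, cognition, satisfaction and, where needed, compliance, but gives the informant no stated part in collecting the primary endpoint. The events of most interest in a study of daytime sedation are ones that a drowsy or cognitively impaired subject may fail to notice, or may not recall after a week. Recall is harder still at a call about 30 days after the last dose. An informant might have seen such an event, but under the text it reaches the adverse event form only if someone volunteers it or staff choose to ask. The protocol neither requires nor forbids asking, so practice may differ between sites.

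**Working it through.** The plan has no figure to reproduce: section 9.3 gives no power calculation, and neither document states how completely subjects report events. The check is therefore mainly of the text.

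**Step 1: which routes to an adverse event record exist, and what each can reach.**

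| Route | Source | Reaches sleepiness, confusion or behaviour change away from the clinic? |
|---|---|---|
| Neutral question to the subject | 7.4.1 | If the subject recognises and recalls it |
| Observed or volunteered by anyone | 7.4.1 | If someone sees it and speaks up |
| New medication as a signal | 7.4.1 | If something was taken for it |
| Laboratory review | 6.3.7 | Not readily |
| At least 60 minutes of observation after dosing | 5.1.3 | No, clinic visits only |
| Orthostatic vital signs, C-SSRS, PD NMS | 6.3.2, 6.3.6, 6.2.5 | PD NMS in part, at scheduled clinic visits |
| Informant ratings on the handheld device | Table S-3 | Sleep and cognition, but no text carries a rating to the adverse event form |

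On the last row, handheld data do not enter the EDC system (10.2, 10.3) and are analysed under a separate SAP (SAP 1). Staff are told to review whether the assessments were completed (Table S-1, footnote i). Handheld collection ends at Week 4.

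At the follow-up call, the first three routes are essentially all that remain. The omission matters most there.

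**Step 2: illustration of a loss equal in all arms.** Let s be the share of true events that the subject's answer brings out. The documents give no value, so s is assumed. Take p = 18%, the quetiapine somnolence figure in section 1.2.2, which the protocol says comes from relatively younger and healthier populations. Planned size is 60/3 = 20 per arm; with 11 randomized (SAP 19) it is about 4. Expected recorded cases are n × p × s. The chance of recording at least one is 1 − (1 − p × s)^n.

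| s | Expected cases, n = 20 | Chance of at least one, n = 20 | Chance of at least one, n = 4 |
|---|---|---|---|
| 1.0 | 3.60 | 0.981 | 0.548 |
| 0.8 | 2.88 | 0.955 | 0.463 |
| 0.6 | 2.16 | 0.898 | 0.367 |
| 0.4 | 1.44 | 0.776 | 0.258 |

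This treats the subject's answer as the only route, so it overstates the loss wherever another route works.

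**Step 3: effect on an arm difference.** Take assumed true rates of 40% and 20%, a difference of 20 points.

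- Equal s of 0.9: 36% − 18% = 18 points, 10% too small.
- Equal s of 0.6: 24% − 12% = 12 points, 40% too small.
- s of 0.6 in the sedated arm and 0.8 in placebo: 24% − 16% = 8 points.
- The reverse, 0.8 and 0.6: 32% − 12% = 20 points, no change.

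The effect on the difference depends on which arm reports less completely, and the documents do not settle that.

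**The case against.** The strongest reply is that capture is wider than the question. A spontaneous informant report must be recorded, staff watch subjects after dosing, and clinicians rate them at visits. That is right. A reader might infer that informant reports are ignored or excluded; the recording rule in 7.4.1 rules that out. What survives is narrower: the informant is not actively asked.

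Second, subjects are screened for reliability. They must consent for themselves, show that they can complete self-reports on a device, and be judged reliably rateable (4.1). Symptoms mainly due to delirium are excluded (4.2). An MMSE of 19 is the floor, and nothing shows it to be typical. This lessens the concern without removing it.

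Third, a reader might infer that sedation effects are biased towards zero by a known amount. The documents do not support that. A sedated subject might report sedation more readily, and Step 3 shows that the reverse pattern leaves the difference unchanged. Any effect concerns adverse event counts, not the dedicated sleepiness and actigraphy measures. The event analysis is descriptive. On the assumed 40% and 20%, the standard error of the difference at 20 per arm is √(0.24/20 + 0.16/20) = 14 points, more than the 12-point shift in the worst case shown. At 11/3 per arm it is √(0.40/3.67) = 33 points.

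Fourth, the informant is not guaranteed to be present. Criterion 4 states willingness, and the schedule has no attendance row. This stands, and the fix has to allow for it, or ascertainment would vary with attendance.

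**Conclusion.** The point holds as one about elicitation. The subject is the only person the documents say to ask about the primary endpoint, although a blinded informant chosen for reliability is part of the design. Some sleepiness, confusion and behavioural events between visits and before the follow-up call may be missed. How many, and whether the loss differs by arm, cannot be derived from the documents; the figures above rest on assumed reporting shares and, in Step 3, assumed event rates. The point does not show that any treatment comparison is distorted in a given direction. Enrolment ended at 11 subjects, so the practical use now is a stated limitation in the report and better wording in the later studies that this pilot is meant to guide.

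**What to change.** In protocol 7.4.1 and 6.4, state that the same nonspecific question is put to the subject and to the informant at each clinic visit and at the safety follow-up call. Ask the informant in person when present and otherwise by telephone, identically in all arms. A field on the adverse event form for the source of each report (subject, informant or observed) is optional: no planned analysis uses it, but it would let the informant's contribution be described.

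The cost is one sentence in 7.4.1, matching text in 6.4, and a few minutes per visit. Somewhat more background Parkinson's symptoms would be recorded in every arm, and comparability with earlier studies would be slightly reduced. Sample size and planned analyses do not change.
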